group and semi-structured interview guides for these meetings consisting of open-ended questions and probes to focus while allowing participants to speak freely. The meeting guides will be adapted from tools used in the formative phase to assess acceptability of the intervention and feasibility of strategies.

E.2.a. Qualitative Analysis Plan: The qualitative data will be analyzed using content thematic analysis.¹⁹ When possible, meetings and interviews will be audiotaped and transcribed verbatim, with accuracy confirmed, and coded using ATLAS.ti version 8.0,²⁰ a powerful analytical tool for qualitative analysis. When taping is not possible, these discussions will be captured through extensive notetaking. [name], an expert in qualitative and mixed methods research will oversee all phases of the qualitative analysis including the data integration phases. Preliminary analysis will include a line-by-line review yielding clusters of data that we will label into brief headings. We will derive codes from these data linked to meeting/interview questions and coding categories. We will summarize coding categories within-cases, then across cases, subsequently cross-classified to yield a rich descriptive analysis.²¹ Finally, we will identify emerging themes both within and across coding categories; and verify a review of data fit. For the key stakeholder meetings/interviews, we will analyze data site by site and then across sites to identify site-specific data as well as overarching themes. In the final analysis stage, we will integrate qualitative and quantitative site/unit-specific data to describe implementation barriers and facilitators. We anticipate that the qualitative data will also reveal factors that influence understanding (e.g., interpretation of serology results, what constitutes meaningful and at-risk contact). In the final analytic phase, we will use informational matrices, a type of joint display²² to integrate the stakeholder qualitative data and the resident outcome data to describe the mechanism of testing and cohorting effectiveness. Methodological rigor²³ throughout all phases of this analysis will be assured by training of research staff who will do initial coding, assessing inter-coder reliability, an audit trail of analytic decisions, regular meetings with experts and member checking, the process by which findings are validated as representative of the experience of the participants.

F. PROJECT MANAGEMENT PLAN AND TIMELINE

Please see Biosketches for qualifications of co-investigators. A GANTT chart is included here. [name] will have responsibility for all aspects of study design and execution. We have already established meetings with ArchCare leadership in developing this proposal. This will serve as an excellent conduit to a rapid launch should this study be funded. His senior research coordinator, [name] is bilingual and has an excellent rapport with facility staff at both MMW and TCC. [name] will work closely with ArchCare leadership and facility staff to coordinate all meetings and will serve as the go-between for the research team and facility staff. [name] has expertise in serologic and PCR testing and will facilitate that process and data interpretation. His close working relationship with his NYU colleagues ensures that new discoveries will more readily be integrated into pilot work where appropriate and deemed to be of benefit. Our team is also benefitted by the counsel and expertise of the NIA IMPACT Collaboratory including, bioethics, dementia, health equity, implementation, stakeholder concerns, and pragmatic statistical design. We will meet periodically with Collaboratory experts for ongoing advice and specific direction where needed.

GANTT Chart - COVID-19 SEROLOGIC SNF STRATEGIES	Month											
	1	2	3	4	5	6	7	8	9	10	11	12
Tasks												
Schedule and hold stakeholder meetings												
IRB application to Advarra												
Conduct additional focus groups, interviews												
Convene Expert Panel												
Establish testing protocol and subject consent												
Build and test REDCap cohort-support tool												
Randomize units and train staff												
Conduct and collect PCR and Serology testing												
Maintain audit and feedback with staff and leadership												
Conduct qualitative analyses												
Conduct quantitative analyses												
Complete final report, manuscripts and large trial application												

References

2. U.S. Centers for Medicare & Medicaid Services. Nursing Home Data Compendium 2015 Edition. Available at: https://www.cms.gov/Medicare/Provider-Enrollment-and-Certification/CertificationandCompliance/Downloads/nursinghomedatacompendium_508-2015.pdf. Accessed June 17, 2020.

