This study is innovative for several reasons: 1) a resident-staff cohorting strategy based on a) completed vaccination; b) prior COVID-19 PCR positive testing; and c) positive serology has to our knowledge, never been utilized for infection control in any healthcare setting; 2) although stakeholder-influenced study designs have been increasingly utilized, employing a multi-stakeholder approach to design a facility-specific testing and cohorting strategy is highly innovative and ensures a greater engagement and fidelity across all involved sectors; 3) a detailed implementation design to capture values, changing attitudes, structural and cultural barriers to a testing and cohorting strategy is also innovative and will greatly serve larger trials and best practice disseminations; 4) comparing primary outcomes and infection rates between those with and without ADRD is novel; and 5) the use of smartphone based technology to facilitate proper cohorting while increasing fidelity is highly innovative and ensures greater capture of deviations from the intended approach. Additionally, this approach can benefit facilities in their effort to increase contact-monitoring amongst staff and residents.

D. METHODS AND APPROACH

D.1. Overview: This one-year cluster-randomized pilot study will be conducted in three phases. We have engaged two NYC facilities as the sites of the proposed study, where (Phase 1: AIM 1 – one month) we will convene all stakeholders (leadership, staff, residents, and their families) and engage a panel of experts to create a feasible, scientifically sound protocols for staff-resident assignments based on serology (if applicable), vaccination and PCR testing protocols, and Implementation monitoring. In the second phase (Aim 2 – two months), we will identify four units (average 40 residents per unit) in each facility. We will stratify the two NHs and then within each SNF, randomly allocate two units to the intervention arm and two units to the control arm (we have confirmed homogeneity across these four units in each SNF supporting no need for further stratification). We will conduct baseline serology and/or PCR COVID-19 tests from residents and staff on all four units in each SNF.

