D.2. Setting and Participants: We are conducting the proposed trial in two nursing facilities in NYC: Mary Manning Walsh (MMW) and Terrence Cardinal Cooke (TCC). Both facilities operate under the umbrella of the ArchCare Organization, a non-profit corporation that owns and operates five nursing facilities in addition to other older age care services. [name] and his team have been actively engaged in a research study (*SLUMBER* R01NR016461-01) in these facilities and others that involves staff education to promote better sleep, work that has led to smartphone-based educational reinforcements, which will support the proposed intervention. Both facilities care for a large proportion (>60%) of residents with dementia. Both facilities are also diverse: 20% LatinX in MMW and 25% African American in TCC and there are 362 and 485 residents in these facilities, respectively. MMW recorded over 30 COVID-19-related deaths by the third week in April (the highest nursing home death rate in New York State at that time) and TCC had more than 20. Both facilities are currently mandating weekly testing of all staff and are conducting their first-wave resident tests for all residents and anyone with symptoms. Plans for repeated resident testing will follow CDC guidelines, which are expected to evolve over the next few months. Intervention participants include four groups: leadership, staff, residents and family. For leadership and family, they will participate in the institution's effort to develop a strategy for reducing COVID-19 infections by providing guidance to testing, staff assignment strategies and ongoing feedback based on periodic process data collection, analysis and reports. Staff and residents will follow the guidelines and requirements of the facility, which will be implemented on two units as a quality improvement initiative.

D.3. Methods for Aim 1:

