D.4.a. Testing Protocol and Data Entry: The facility will conduct periodic PCR testing based on CDC guidance and will test additionally based on individual symptom or exposure-related concerns. Modifications to the testing strategy will be based on collaboration between facility leadership and our infectious disease expert. Given the discomfort of a deep nasopharyngeal swab, we will use, if deemed acceptable at the time the pilot study is conducted, a saliva-based PCR test to identify active infection and the frequency of testing will be based on a collaborative decision between our infection disease expert ([name]) and facility leadership. Collection of completed vaccination and/or prior COVID-19 PCR positive testing records or positive serology testing will occur at baseline and at three and six months but the frequency may be modified based on new discoveries as our understanding of this virus evolves. The laboratory providing results will present testing results to the facility in a timely manner, if possible, and those results will also be transmitted to our study team. Although it is best that the facility maintain responsibility for populating their health records, we will confirm their interest in using our REDCap database and we will closely monitor those entries to ensure accuracy and present timely feedback using a standard audit and feedback process. We have successfully used this approach in other nursing home studies focused on depression care.¹⁸ For any resident moving into an intervention unit, the default status will be 'COVID-19 negative' until vaccination completion records or prior COVID-19 PCR positive status is known, or if serology testing is performed. We also anticipate completed vaccination, prior COVID-19 PCR positive testing and serology results will be collected at baseline, three and six months but a different set of frequencies for testing will also be considered. Test results will be maintained at the level of the individual resident and labeled for easy recognition by facility and unit. Weekly meetings between study team, the facility designated data manager, and staff leadership for each intervention unit (n=4) will ensure data accuracy and quality.

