D.5.a. Randomization of Units: 40-bed facility units are the unit of randomization and we will randomize within individual SNFs to select each intervention unit. Should we identify specific unit-level characteristics that are not consistent across units (we have been assured there are none) and may influence our outcomes (such as median age, other demographics or unit size) we will conduct a stratified randomization. We recognize there may be some contamination between staff/residents between intervention/control units but will do our best and monitor this “contamination” as one of our implementation fidelity outcomes.

D.5.b. Staff-Resident Assignment Strategy: Within individual intervention units, we will pair care-partners (staff) with individual residents, based on 1) completed vaccination; 2) prior COVID-19 PCR positive testing; and 3) positive serology (if applicable). For serology testing, antibody negative will be paired with antibody positive as well as antibody-positive with anti-body positive if the frequency of antibody-positive residents and staff is high. Prior known COVID-19 infection and recovery in the absence of vaccination will still require serology testing as we do not yet know how to anticipate antibody development and resilience. Contact between two or more antibody-negative and unvaccinated individuals (and no history of positive PCR) will be restricted such that no antibody negative, unvaccinated individual (and no history of positive PCR) will intentionally interact with another antibody-negative, unvaccinated person (and no history of positive PCR), regardless of individual type (resident or staff). We anticipate that high staffing ratios (more residents with fewer staff) that require the responsibility of one staff person to care for several residents will present considerable challenges to achieving full fidelity, particularly on overnight shifts. Although strict cohorting is a primary implementation goal, we anticipate less than perfect fidelity. Nonetheless, we believe that any reduction in unnecessary exposure will reduce the risk of disease transmission and may lead to meaningful outcomes. Ensuring greatest fidelity will require full engagement of clinical leaders (nursing leads) at the unit level but these leaders will require real-time data for making staffing decisions. These data should also be available to front-line staff so that there is less opportunity for misinformation or lack of information to inform decisions.

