E.1. Quantitative Analyses: The ultimate goal of developing a serologic strategy is to reduce COVID-19 infection rates and hospitalizations. In this pilot phase, where the focus is informing the design of a larger pragmatic RCT, a key focus will be on the ability to measure the outcomes, incident cases of COVID-19 and hospitalizations, in a pragmatic way using administrative data only. Once we have successfully collected these data, we will estimate incident rate ratios using Bayesian Poisson models that include resident length of stay in the nursing home. The Bayesian model provides a posterior probability distribution of the effect of serologic strategy on incidence and hospitalizations. A strength of this analytic approach is that we will be able to conduct ongoing interim analyses to understand if and how the strategy is working as we conduct the study.

The COVID-19 analysis will be conducted at the level of the nursing home unit using this model:

$$Y_i \sim \text{Poisson}(\lambda_i)$$

$$\log(\lambda_i) = \beta_0 + \beta_1 T_i + \log(R_i)$$

Y_i is the number of incident cases for nursing home unit i , $i \in [1, 2, \dots, 8]$. T_i is an intervention indicator, $T_i = 1$ if unit i is using the serologic strategy, $T_i = 0$ otherwise. R_i is the total number resident-days for unit over the 6-month observation period. The parameter λ_i represents the modeled mean for site, and λ_i/R_i is the incidence rate, represented as the number of infections per resident-day. β_1 is the effect of interest: the incidence rate ratio. We will assume an uninformative prior distribution for β_1 . The model for hospitalizations will be developed in the same manner. Both analyses will be conducted using the latest version of R, which is currently 4.0.0 (R Foundation for Statistical Computing, Vienna, Austria).

E.2. Qualitative Analyses: Overview of Qualitative Methodology: This project includes qualitative data from key stakeholder meetings and interviews about: 1) perceptions of the testing program and implementation strategies; 2) perceptions about staff-resident assignment strategies; 3) barriers/facilitators toward program implementation and sustainability including the impact of staffing changes on resident behaviors for those with ADRD. Because much of this work is implementation and feasibility-specific, meetings will often be both information giving and soliciting of other details, e.g., how is testing being conducted currently. We will use focus

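### Units are randomised within facility, but neither rate model has a facility term, so the rate ratio can shift if the arms' resident-days split differently across the two homes.

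*Combined protocol and SAP*

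**What the plan says.** Allocation is stratified. Section D.1 states "We will stratify the two NHs and then within each SNF, randomly allocate two units to the intervention arm" and two to control. Section D.5.a repeats that "we will randomize within individual SNFs to select each intervention unit". This gives eight units, two per arm in each of two facilities.

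The only quantitative model is in section E.1: log(λ_i) = β0 + β1·T_i + log(R_i), fitted to the eight unit counts with an uninformative prior on β1. The offset is observed exposure: "R_i is the total number resident-days for unit over the 6-month observation period". For the second outcome, "The model for hospitalizations will be developed in the same manner". No section adds facility to either model.

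Section D.1 says homogeneity was confirmed across the four units in each facility. That compares units within a facility. It does not compare one facility with the other.

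Elsewhere the protocol leaves room for the sites to differ:

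- Section C describes "employing a multi-stakeholder approach to design a facility-specific testing and cohorting strategy".
- Section D.4.a says "Modifications to the testing strategy will be based on collaboration between facility leadership and our infectious disease expert".
- Section E.2.a, for the qualitative data only, says "we will analyze data site by site and then across sites to identify site-specific data".

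**The concern.** When allocation is stratified, the analysis would normally include the stratum. Here it does not. The offset corrects for how many resident-days each arm has, but not for which facility they come from.

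Equal numbers of units per arm do not settle this, because R_i is occupancy accrued over six months and can drift through deaths, transfers and vacancies. If facility rates differ and one arm happens to have more of its resident-days in the higher-rate home, part of the facility difference appears as an intervention effect.

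There is a second, conditional consequence. If a dispersion or between-unit variance term were added to the model, the facility difference would be counted as unit-to-unit noise. The interval would widen, and the between-unit variation passed on to the design of the larger trial would be too high.

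**Working it through.** The plan gives no event rate, expected effect or power, so there is no stated figure to reproduce.

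**Inputs from the plan.** Two facilities, two units per arm in each, about 40 residents per unit, six months, and the E.1 model with a flat prior.

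**Assumed inputs.** Facility rate ratio r = 1.5 to 2, and 32 events in total (4 per unit × 8 units).

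Section D.2 gives a rough indication that the facilities may differ: "MMW recorded over 30 COVID-19-related deaths by the third week in April" among 362 residents, against more than 20 among 485 at the other home. That is 30/362 = 8.3% against 20/485 = 4.1%, a ratio of about 2.0. Both counts are open-ended and come from the first wave, so they do not fix r for the trial period.

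**Step 1: what the model estimates.** With a flat prior the estimate is close to the crude rate ratio. Let s1 and s0 be the shares of intervention and control resident-days in the higher-rate facility. If the true within-facility ratio is θ, the crude ratio tends to θ·[s1·r + (1 − s1)] / [s0·r + (1 − s0)]. When s1 = s0 this equals θ for any r, so omission does no harm. That holds even if the arms are unequal, provided they are unequal in the same proportion in both homes.

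**Step 2: opposite imbalance.** Let intervention exposure be (1 + d) and control (1 − d) times the mean in the higher-rate facility, and the reverse in the other. With θ = 1 the estimate is [(1 + d)r + (1 − d)] / [(1 − d)r + (1 + d)].

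| d | r = 1.5 | r = 2 | log shift ÷ 0.354 at r = 2 |
|---|---|---|---|
| 5% | 2.525/2.475 = 1.020 | 3.05/2.95 = 1.034 | 0.09 |
| 12.5% | 2.5625/2.4375 = 1.051 | 3.125/2.875 = 1.087 | 0.24 |
| 20% | 2.6/2.4 = 1.083 | 3.2/2.8 = 1.143 | 0.38 |

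In Poisson fits to expected counts, the model with a facility indicator returned the true ratio in every scenario tried.

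**Step 3: standard error.** With 16 events per arm, SE = √(1/16 + 1/16) = 0.354. With the facility term it is √{4/[32(1 − d²)]}: 0.354 at d = 0 and at 5%, 0.356 at 12.5% and 0.361 at 20%. The increases are about 0.1%, 0.7% and 2%. With equal exposure the term costs nothing.

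**Step 4: how large a shift chance produces.** Drawing the eight units' resident-days independently (200,000 draws, r = 2), the SD of the log shift is 0.024 at a coefficient of variation (CV) of 10% and 0.048 at 20%. The 95% ranges around a true 1.00 are about 0.95 to 1.05 and 0.91 to 1.10. The distribution is centred on no shift.

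**Step 5: only if dispersion is modelled.** Simulated with 4 to 8 cases per unit, residual between-unit CV of 0.3 to 0.5, and Pearson-scaled t-intervals (6 df without facility, 5 with):

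- Omitting facility widens the interval by about 1% to 7% at r = 1.5 and 10% to 26% at r = 2. If the dispersion is not allowed below 1, the figures are about −1% to 5% and 7% to 20%.
- The apparent between-unit CV is √{(1 + cv²)(1 + [(r − 1)/(r + 1)]²) − 1}. For cv = 0.3 and r = 2 this is √(1.09 × 1.111 − 1) = 0.46. A true 0.3 or 0.5 reads as 0.37 or 0.55 at r = 1.5, and as 0.46 or 0.62 at r = 2.
- Under the Poisson model as planned, the width ratio is 1.000 in every setting.

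**The case against.** The strongest reply is that this hardly matters in a pilot. At r = 2 and a CV of 10%, the root mean squared error of the log rate ratio goes from 0.3536 to √(0.3536² + 0.024²), about 0.354, a rise of about 0.2%. The 95% interval already spans a factor of about 2 either side (exp(1.96 × 0.354) = 2.0). Section D.1 expects no statistical significance, and section E.1 puts measuring the outcomes first.

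The larger shifts also need unlikely inputs. An opposite imbalance of 12.5% or more arises in about 0.05% of draws at a CV of 10% and 8% at a CV of 20%. For 20% or more the figures are none of 200,000 draws and 0.6%. Section D.5.a reports an assurance that unit characteristics, with unit size among its examples, are consistent, and promises stratified randomisation if they are not. In 40-bed units, a 20% imbalance would mean roughly 40 against 27 residents on average in one home and the reverse in the other.

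The evidence that incidence will differ by facility is thin. One operator runs both homes, both were under the same staff testing mandate, and later testing follows government guidance. Tailoring to stakeholders and site-by-site qualitative coding say nothing direct about infection rates. The dispersion results concern a model that the plan does not contain.

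All of this stands as a limit on size. It does not show that facility is accounted for: the unit-size safeguard acts at randomisation and does not control occupancy afterwards, and nothing in the plan says the two homes have equal rates.

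**Conclusion.** The concern holds. Facility is a randomisation stratum and is missing from both the infection and the hospitalisation model. Under the planned Poisson model, the result is a possible chance shift in the rate ratio that requires both a facility rate difference and unequal resident-day shares. At a facility ratio of 2 it is typically within about 5% either way at a CV of 10%, or about 10% at a CV of 20%. That is small beside a standard error of 0.354, and the planned interval width is unaffected when exposure is balanced. These sizes rest on the assumed facility ratio, event total and spread of resident-days.

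The reason to act is that the correction is nearly free and that this pilot is meant to inform a larger trial, which could inherit both the model and any between-unit variance estimated from it. It should be changed, but it does not threaten the pilot.

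**What to change.** In section E.1, replace the linear predictor in both models with log(λ_i) = β0 + β1·T_i + β2·Facility_i + log(R_i), with a weakly informative prior on β2. State this before outcome data are examined, so that the term cannot be seen as a post hoc choice. Report resident-days by arm within each facility, so that readers can see whether the shares differ.

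The facility term does not deal with overdispersion between units, which needs its own provision. Any between-unit variance carried into the larger trial's design should be the within-facility value.

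The cost is a sentence of SAP text and one parameter. The effect on the standard error is nil with balanced exposure and about 2% at the most extreme imbalance shown. If dispersion is also modelled and the facilities turn out not to differ, intervals are about 4% to 5% wider.

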It should not be surprising that COVID-19 infections in SNFs are widespread and death due to infection is common. Death is likely to be even higher in residents with ADRD who are unable to report symptoms, thus delaying needed medical care. Long-term care facility deaths have been among the largest proportion of state reported deaths and several-fold higher when considered as a proportion of those infected who die.⁵ Recognizing that the U.S. has now exceeded 100,000 deaths overall due to COVID -19, as of May 2020, nursing home residents accounted for more than one-third of the then 80,000 deaths in the U.S.¹⁴ How many who have died and had ADRD is unknown. The best-known example was the first – a facility in King County, Washington when the first index case was identified on February 28th, 2020. By March 18th 167 persons were diagnosed and linked to this index case within two Washington Counties. Among 118 tested facility residents, 101 were positive for COVID-19 and 35 had died.⁹ Over half of all residents were hospitalized. Fifty health care personnel, another constituency of great concern, had COVID-19. In New York State, the site for this pilot study, state officials identified 86 facilities with at least five COVID-19 related fatalities and over 300 New York facilities had at least one.¹¹ But because the federal government did not require reporting prior to May, underreporting is likely to be systemic and post-dates the period of high disease prevalence in March and April.¹⁵

Suspected asymptomatic spread also appears to be high in these settings,⁸ which requires a more rigorous approach for isolation of affected residents from those who are not and removal of staff with identified infections. Some facilities such as those in this pilot (where ADRD prevalence is high) are engaged in frequent testing of residents and staff, a practice which leads to isolation of all affected residents, and reductions in personal care. This approach also results in cessation of meaningful activities and harmful social isolation, further compounded by greater staffing shortages. While the heightened risks for SNF residents are indisputable, less attention has

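### The E.1 Poisson model has no between-unit variance, so its credible intervals are too narrow if units in a facility differ beyond Poisson variation: slightly at very few cases, badly after a single-unit outbreak

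*Combined protocol and SAP*

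**What the plan says.** Section E.1 introduces its only outcome model with "The COVID-19 analysis will be conducted at the level of the nursing home unit using this model". The model is Y_i ~ Poisson(lambda_i), with log(lambda_i) = beta_0 + beta_1 T_i + log(R_i), for eight units. T_i is the arm and R_i the unit's resident-days over six months. The prior on beta_1 is described only as uninformative. Hospitalizations are to be modelled the same way. E.1 also intends to examine the posterior repeatedly while the study runs, to judge whether the strategy works.

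On the design, D.1 says "We will stratify the two NHs and then within each SNF, randomly allocate two units to the intervention arm", with the other two units as controls. D.5.a says "40-bed facility units are the unit of randomization and we will randomize within individual SNFs to select each intervention unit". D.1 also says "we have confirmed homogeneity across these four units in each SNF supporting no need for further stratification".

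On how infection spreads in these settings, section B says of one outbreak: "By March 18th 167 persons were diagnosed and linked to this index case within two Washington Counties". It adds: "Among 118 tested facility residents, 101 were positive for COVID-19 and 35 had died".

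No section supplies a unit effect, an overdispersion parameter, a robust variance or a facility term.

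**The concern.** A Poisson model sets the variance of each unit's count equal to its mean. In a trial that randomises whole units, the treatment contrast also carries any real difference in infection rate between units. Using eight unit-level rows does not allow for that, because nothing in the model lets two units in the same arm and facility have different underlying rates.

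Infections are not independent events: one introduction can seed many cases in a unit. The outbreak in section B predates vaccines and concerns a whole facility, so it gives no between-unit CV, but it shows linked cases. The homogeneity statement in D.1 supports a decision not to stratify further. It says nothing about a chance introduction into one unit.

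At stake is an overconfident posterior for incidence. An outbreak in one control unit could look like good evidence that the strategy works, including at an interim look.

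**Working it through.** The plan states no sample size, event count, power or between-unit variance, so it has no figure to reproduce. Case counts and CVs below are assumptions.

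**1. The model uses only arm totals.** Apart from a constant, the log-likelihood is the sum over arms of Y_a·log(rate_a) − rate_a·R_a, where Y_a and R_a are the arm's total cases and resident-days. The split across units drops out. For 3 v 22 cases, the likelihoods with the 22 spread out or all in one unit differ only by a constant.

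**2. Size of the shortfall.** Let mu be expected cases per unit and CV the within-facility variation in unit rates. An arm of four units has mean 4mu and variance 4mu + 4mu²CV². The log rate then has variance of about 1/(4mu) + CV²/4, but the model counts only 1/(4mu). The ratio of true to modelled standard error is sqrt(1 + mu·CV²). At mu = 2, CV = 1 it is sqrt(3) = 1.73. At mu = 8, CV = 1 it is sqrt(9) = 3.

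Simulated coverage of the nominal 95% interval (40,000 trials per cell, true rate ratio 1, four v four units, equal resident-days, equal facility rates, gamma heterogeneity, arm-rate posterior Gamma(Y+0.5, R)):

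| Cases per 40-bed unit (attack rate) | CV 0 | CV 0.5 | CV 1 |
|---|---|---|---|
| 0.5 (1.25%) | 96% | 95% | 92% |
| 1 (2.5%) | 95% | 93% | 85% |
| 2 (5%) | 95% | 89% | 75% |
| 4 (10%) | 95% | 83% | 62% |
| 8 (20%) | 95% | 75% | 49% |

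Lognormal heterogeneity at CV 1 gives 92/86/78/67/54%. At 0.25 events per unit, plausible for hospital transfers, coverage is 97% or more for CV up to 1. If instead each unit has a 25% chance of an outbreak averaging 10 cases (20 expected in total), coverage is 43%.

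**3. One data set, two splits.** Arm totals are 4 v 12. The splits are chosen as contrasts, not forecasts. The comparison model adds a unit effect with a half-normal(0,1) prior on its SD, tau, and a facility term.

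| Split | Model | IRR (95% interval) | Pr(IRR<1) |
|---|---|---|---|
| Either | Plan | 0.34 (0.10–0.97) | 0.98 |
| 1,1,1,1 v 3,3,3,3 | With unit effect | 0.34 (0.09–1.13) | 0.96 |
| 1,1,1,1 v 1,9,1,1 | With unit effect | 0.43 (0.09–2.45) | 0.85 |

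In the outbreak split, Pr(IRR<1) is 0.90, 0.85 and 0.82 under half-normal scales 0.5, 1 and 2.

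**4. Does a unit effect restore coverage?** A separate run used 2,000 null trials per cell, a facility rate ratio of 2 and an N(0, 2.5²) prior on beta_1 in both models. Its plan coverages differ from the grid by up to about 3 points because of those settings.

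| Cases per unit / CV | Plan | With unit effect and facility term |
|---|---|---|
| 0.5 / 1 | 93% | 97% |
| 1 / 0.5 | 92% | 97% |
| 1 / 1 | 82% | 95% |
| 4 / 0.5 | 83% | 97% |
| 4 / 1 | 60% | 94% |
| 8 / 0.5 | 74% | 97% |
| 8 / 1 | 47% | 94% |

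At CV 1 and 1/2/4/8 cases, half-normal(0,0.5) covers 90/89/87/87% and half-normal(0,2) covers 97/98/96/97%.

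**5. Facility term: a separate, smaller point.** A pure facility difference cancels under two v two allocation with equal resident-days. Coverage stays at 94–96% with a facility ratio of 4. It can bias the IRR if resident-days are unbalanced. For a rough ratio, D.2 says "MMW recorded over 30 COVID-19-related deaths by the third week in April", more than 20 at the other facility, and "there are 362 and 485 residents in these facilities, respectively". That gives (30/362)/(20/485) = 2.0, from two lower bounds. With resident-days 10% out of balance in opposite directions, the null IRR is (0.9 + 1.1×2)/(1.1 + 0.9×2) = 1.07, or (0.9 + 1.1×4)/(1.1 + 0.9×4) = 1.13 at ratio 4. A 5% imbalance gives 1.03 and 1.06.

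Once a unit effect is present, leaving out facility inflates tau. With no within-facility heterogeneity, the log-IRR interval widens from 1.43 to 1.78 (8 cases, ratio 2) and from 1.53 to 2.80 (8 cases, ratio 4).

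**The case against.** The strongest reply is that this is a pilot meant to inform a larger trial. The plan expects few cases (section E overview), does not expect significance (D.1), and ties no threshold or stopping rule to the posterior. At 0.5 cases per unit the plan's interval covers 92–96% for CV up to 1. At 1 case and CV 0.5 the miss is about 3 points low under the plan and 2 points high under the remedy. The worst figures need attack rates of 10–20% together with CV 1, and the documents support neither number. With eight units, tau is weakly estimated, so the wider interval partly reflects a chosen prior. Weekly infection review (D.3.a) and the unit-specific data in the final analysis (E.2.a) would probably reveal an outbreak.

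Most of this stands as a limit on the harm. It does not make the reported interval right. Omitting the unit effect fixes tau at exactly zero, which is itself a strong prior, and even half-normal(0,0.5) covers far better at CV 1. A pilot for a cluster trial also has reason to report what little it learns about between-unit variation.

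One further point stands. D.5.c allows staff to move between the intervention units, and D.5.a expects some contamination between arms. Both can correlate units, and an independent unit effect would not capture that.

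**Conclusion.** The concern holds. The omission is certain: the model is written out in full and nothing elsewhere adds between-unit variance. The size of the harm is conditional. It is negligible if units within a facility share one rate, small at about 0.5 cases per unit, and serious at several cases per unit with CV near 1 or when one unit has an outbreak. For hospital transfers, which are likely to be rarer, it is smaller still. The coverage figures assume independent units, equal resident-days and no true effect. This should be changed before analysis, though it does not threaten the pilot's feasibility aims.

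**What to change.** In E.1, for both outcomes and at every interim look, use log(lambda_i) = beta_0 + beta_1 T_i + beta_2 Facility_i + u_i + log(R_i), with u_i ~ N(0, tau²), or a negative binomial model with the same terms.

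- State every prior, for example half-normal(0,1) on tau and N(0, 2.5²) on beta_1, and also those for beta_0 and beta_2. If uninformative means flat for beta_1, the posterior is improper when an arm has no cases. At 0.5 cases per unit (2 per arm) that happens with probability 1 − (1 − exp(−2))² = 0.25.
- Repeat the analysis with half-normal(0,0.5) and half-normal(0,2) on tau.
- Report the eight unit-level rates and the posterior of tau beside its prior. Say that tau will be imprecise and sensitive to its prior.
- Note that staff movement and contamination may correlate units in ways this model does not capture.

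The change needs SAP wording and a few lines of code, and no new data. The price is wider intervals even when units are alike. With no heterogeneity, median log-IRR width goes from 4.33 to 4.54 at 0.5 cases per unit, 2.99 to 3.58 at 1, 2.05 to 2.71 at 2, 1.43 to 2.00 at 4 and 1.00 to 1.43 at 8. Coverage is then 97–100%. At few cases tau mostly returns its prior: at 1 case per unit and CV 0.5, its median 95% interval was 0.03–1.83 against a prior of 0.03–2.24.
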